8.4. Adverse Events (AEs) Serious Adverse Events (SAEs), and Other Safety Reporting

The definitions of AEs or SAEs can be found in Section [10.3](#).

The definitions of device-related safety events, ADEs, SADEs, and device deficiencies can be found in Section [10.7](#).

Adverse events will be reported by the participant.

The investigator and any qualified designees are responsible for detecting, documenting, and recording events that meet the definition of an AE or SAE and remain responsible for following up all events (see Section [7](#)).

The method of recording, evaluating, and assessing causality of AEs and SAEs and the procedures for completing and transmitting SAE reports are provided in Section [10.3](#).

8.4.1. Time Period and Frequency for Collecting AE, and SAE Information

- All AEs/SAEs will be collected from the start of intervention until the last visit at the time points specified in the SoA (Section [1.3](#)). However, any SAEs assessed as related to study participation (e.g., study intervention, protocol-mandated procedures, invasive tests, or change in existing therapy) or related to a GSK product will be recorded from the time a participant consents to participate in the study.
- Medical occurrences that begin before the start of study intervention but after obtaining informed consent will be recorded as Medical History/Current Medical Conditions not as AEs.
- All SAEs will be recorded and reported to the sponsor or designee immediately, and under no circumstance should this exceed 24 hours, as indicated in [Appendix 3](#). The investigator will submit any updated SAE data to the sponsor within 24 hours of it being available.
- Investigators are not obligated to actively seek information on AEs or SAEs after conclusion of study participation. However, if the investigator learns of any SAE, including a death, at any time after a participant has been discharged from the study, and he/she considers the event to be reasonably related to the study intervention or study participation, the investigator must promptly notify the sponsor.

8.4.2. Method of Detecting AEs and SAEs

Care will be taken not to introduce bias when detecting AEs and/or SAEs. Open-ended and non-leading verbal questioning of the participant is the preferred method to inquire about AE occurrence.

8.4.3. Follow-up of AEs and SAEs

After the initial AE/SAE report, the investigator is required to proactively follow each participant at subsequent visits/contacts. All SAEs will be followed until the event is resolved, stabilized, otherwise explained, or the participant is lost to follow-up (as defined in Section 7.3). Further information on follow-up procedures is given in Section 10.3.

8.4.4. AESIs

Adverse events of special interest include:

- Allergic reactions including anaphylaxis

Note: these events will be assessed by the investigator as to whether they meet the diagnostic criteria for anaphylaxis as outlined by the 2006 NIAID/ FAAN Second Symposium on Anaphylaxis [[Sampson, 2006](#)] ([Appendix 6](#))

- Type III hypersensitivity (immune complex disease/vasculitis) reactions
- Local injection site reactions
- QTc prolongation

See Section 2.3.1 for additional details.

8.4.5. Regulatory Reporting Requirements for SAEs

- Prompt notification by the investigator to the sponsor of an SAE is essential so that legal obligations and ethical responsibilities towards the safety of participants and the safety of a study intervention under clinical investigation are met.
- The sponsor has a legal responsibility to notify both the local regulatory authority and other regulatory agencies about the safety of a study intervention under clinical investigation. The sponsor will comply with country-specific regulatory requirements relating to safety reporting to the regulatory authority, IRBs/IECs, and investigators.
- An investigator who receives an investigator safety report describing an SAE or other specific safety information (e.g., summary or listing of SAEs) from the sponsor will review and then file it along with the IB and will notify the IRB/IEC, if appropriate according to local requirements.
- Investigator safety reports must be prepared for suspected unexpected serious adverse reactions according to local regulatory requirements and sponsor policy and forwarded to investigators as necessary.

8.4.6. Pregnancy

- Details of all pregnancies in female participants will be collected after administration of study intervention and until 30 weeks after the administered dose of study intervention.
- If a pregnancy is reported, the investigator will record pregnancy information on the appropriate form and submit it to GSK within 24 hours of learning of the female participant pregnancy. While pregnancy itself is not considered to be an AE or SAE, any pregnancy complication or elective termination of a pregnancy for medical reasons will be reported as an AE or SAE.
- Abnormal pregnancy outcomes (e.g., spontaneous abortion, fetal death, stillbirth, congenital anomalies, ectopic pregnancy) are considered SAEs and will be reported as such.
- The participant will be followed to determine the outcome of the pregnancy. The investigator will collect follow-up information on the participant and the neonate and the information will be forwarded to the sponsor.
- Any poststudy pregnancy-related SAE considered reasonably related to the study intervention by the investigator will be reported to the sponsor as described in Section 8.4.5. While the investigator is not obligated to actively seek this information in former study participants, he or she may learn of an SAE through spontaneous reporting.

8.4.7. Medical Device Deficiencies

Medical devices (SSD and autoinjector) are being provided for use in this study as a delivery method for depemokimab injections. To fulfill regulatory reporting obligations worldwide, the investigator is responsible for the detection and documentation of events meeting the definitions of device deficiency that occur during the study with such devices.

The definition of a medical device deficiency can be found in Section 10.7.

NOTE: Deficiencies fulfilling the definition of an AE/SAE will also follow the processes outlined in Section 10.3 of the protocol.

8.4.7.1. Time Period for Detecting Medical Device Deficiencies

- Medical device deficiencies that result in an incident will be detected, documented, and reported during all periods of the study in which the medical device is used.
- If the investigator learns of any device deficiency at any time after a participant has been discharged from the study, and such a device deficiency is considered reasonably related to a medical device provided for the study, the investigator will promptly notify the sponsor.
- The method of documenting Medical Device Incidents is provided in Section 10.7.

8.4.7.2. Follow-up of Medical Device Deficiencies

- Follow-up applies to all participants, including those who discontinue study intervention or the study, and associated persons.
- The investigator is responsible for ensuring that follow-up includes any supplemental investigations as indicated to elucidate the nature and/or causality of the deficiency.
- New or updated information will be recorded on the originally completed form with all changes signed and dated by the investigator.

8.4.7.3. Prompt Reporting of Medical Device Deficiencies to the Sponsor

- Device deficiencies will be reported to the sponsor within 24 hours after the investigator determines that the event meets the protocol definition of a device deficiency.
- The Medical Device Deficiency Report Form will be sent to the sponsor by email. If email is unavailable, then fax should be utilized.
- The sponsor will be the contact for the receipt of device deficiency reports.

8.4.7.4. Regulatory Reporting Requirements for Device Deficiencies

- The investigator will promptly report all device deficiencies occurring with any medical device provided for use in the study in order for the sponsor to fulfill the legal responsibility to notify appropriate regulatory authorities and other entities about certain safety information relating to medical devices being used in clinical studies.
- The investigator, or responsible person according to local requirements (e.g., the head of the medical institution), will comply with the applicable local regulatory requirements relating to the reporting of device deficiencies to the IRB/IEC.

8.5. Pharmacokinetics**8.5.1. Blood Sample Collection**

Blood samples for determination of depemokimab plasma concentrations will be collected at the time points indicated in the SoA (Section 1.3). Each PK sample must be collected as close as possible to the planned time relative to when the dose is administered to the participant (which is 0 hour on Day 1). The actual date and time of each blood sample collection will be recorded in the eCRF.

Details on PK blood sample collection, processing, storage, and shipping procedures will be provided in the SRM.

8.5.2. Sample Analysis

Sample analysis will be performed under the control of BIB, GSK. Concentrations of depemokimab will be determined in plasma samples using a validated bioanalytical method.

8.6. Pharmacodynamics

Pharmacodynamics are not evaluated in this study

8.7. Genetics

Genetics are not evaluated in this study.

8.8. Biomarkers

Biomarkers are not evaluated in this study.

8.9. Immunogenicity Assessments

Antibodies to depemokimab will be collected at the time points specified in the SoA (Section 1.3). The actual date and time of each blood sample will be recorded. Details for immunogenicity blood sample collection, processing, storage, and shipping will be provided in the SRM.

Sample analysis will be performed under control of BIB, GSK. The presence of anti-depemokimab antibodies will be determined in serum samples using a validated bioanalytical method, with a tiered analyses approach using a screening assay, confirmation assay, and titer assay and a validated NAb assay. If necessary, further immune response characterization may be performed as needed.

8.10. Health Economics OR Medical Resource Utilization and Health Economics

Health economics/medical resource utilization and health economics] parameters are not evaluated in this study.

9. STATISTICAL CONSIDERATIONS

9.1. Statistical Hypotheses

This study is designed to estimate the relative bioavailability of depemokimab 100 mg administered subcutaneously via an autoinjector compared to a SSD. No formal hypotheses will be tested. For C_{max} and $AUC(0-\infty)$, point estimates and corresponding two-sided 90% CIs will be constructed for the ratio of the geometric mean of the autoinjector to SSD.

An additional assessment will be made by comparing observed 90% CI of geometric mean ratio to the standard bioequivalence reference range of 0.8 to 1.25.

9.2. Analysis Sets

For the purposes of analysis, the following analysis sets are defined:

Population	Definition/Criteria
Screened	All participants who are screened.
Safety	All participants who take at least 1 dose of study intervention. Participants will be analysed according to the intervention they actually received.
Pharmacokinetic	All participants in the Safety Population for whom at least 1 evaluable pharmacokinetic sample will be obtained and analysed. Participants will be analysed according to the intervention they actually received.

9.3. Statistical Analyses

9.3.1. General Considerations/Definitions

The SAP will include a more technical and detailed description of the statistical analyses described in this section. This section is a summary of the planned statistical analyses of the primary, secondary, and exploratory endpoints.

9.3.2. Primary Endpoint(s)/Estimand(s) Analysis

Pharmacokinetic Analysis

Plasma depemokimab concentration-time data will be analysed by PPD, under the oversight of the Clinical Pharmacology Modeling & Simulation department within GSK, using noncompartmental methods with Phoenix WinNonlin Version 8.0 or higher. Statistical analysis will be performed by Veramed, under the oversight of Biostatistics, GSK. Calculations will be based on the actual sampling times recorded during the study.

Based on the individual concentration-actual time data the following PK parameters will be estimated as data permit:

- $AUC(0-\infty)$ – Area under the concentration-time curve from time zero extrapolated to infinity

- AUC(0-t) – Area under the concentration-time curve from time zero to time of last observed quantifiable concentration
- C_{max} – Maximum observed plasma concentration
- T_{max} – Time to maximum observed plasma concentration
- CL/F – Apparent clearance following extravascular administration
- V_d/F – Apparent volume of distribution following extravascular administration
- λ_z – Terminal elimination rate constant
- t_{1/2} – Terminal elimination half-life
- T_{last} – Time of last measurable plasma concentrations
- %AUC_{ex} – Percentage of AUC(0-inf) due to extrapolation from T_{last} to infinity

Pharmacokinetic data will be presented in graphical and/or tabular form and will be listed and summarized descriptively by treatment group, and by injection site.

Endpoint	Statistical Analysis Methods
Primary	
The analysis for the primary PK endpoints will be performed for the PK Population.
 
Pharmacokinetic analysis will be performed to compare the relative bioavailability of a single subcutaneous dose of 100 mg depemokimab administered via an autoinjector compared to a single subcutaneous dose of 100 mg depemokimab administered via SSD.
 
Based on the individual concentration-time data the following primary plasma PK parameters will be estimated:
 
C_{max} and AUC(0-inf)
 
Analysis will be performed on the natural logarithms of AUC(0-inf) and C_{max} using a fixed-effects analysis of covariance model, with treatment and injection site as categorical covariates, and baseline weight as a continuous covariate fitted on the log scale. Effects will be estimated, and 90% CIs will be constructed for the following treatment comparisons:
 
Treatment B (Autoinjector) versus Treatment A (SSD)
 
Point estimates and 90% CIs for treatment differences on the log scale derived from the model will be exponentiated to obtain estimates for geometric mean ratios and CIs on the original scale.

Secondary	
The analysis for the secondary PK endpoints will be performed for the PK Population.

Endpoint	Statistical Analysis Methods
	Summary statistics for AUC(0-t), CL/F, Vz/F, λ_z , and t _{1/2} , (arithmetic mean, geometric mean, median, 95% CI [arithmetic and geometric], standard deviation [arithmetic and on ln-scale], minimum, maximum, and geometric CV). For T _{max} and T _{last} , median, minimum, and maximum only will be reported for each treatment group.

Further details of the PK analysis are provided in the SAP.

9.3.3. Safety Analyses

All safety analyses will be performed on the Safety Population.

Summaries of safety data will include AEs, SAEs, change from baseline of vital signs, ECGs, and laboratory parameters along with hepatobiliary abnormalities. Adverse events will be coded using the MedDRA coding dictionary and will be grouped by SOC and summarized by preferred term and treatment. Adverse events will be summarized by frequency and percentage of participants, by SOC and preferred term within each group. Separate summaries will be provided for all AEs, drug-related AEs, SAEs, and AEs leading to withdrawal from the study.

The positive rate of ADAs following a 100 mg depemokimab before and after administration will be summarized and listed based on the safety population. Details will be presented in the SAP.

9.3.4. Exploratory Analysis

To assess the pharmacodynamics of a single subcutaneous dose of depemokimab delivered with a safety syringe or an autoinjector in healthy adult participants, the ratio to baseline of the eosinophil count will be summarized by treatment group with descriptive statistics.

To assess the pharmacokinetics of a single subcutaneous dose of depemokimab delivered in the upper arm, abdomen, or thigh in healthy adult participants, the measured depemokimab plasma concentration at planned visits will be summarized with descriptive statistics. Additionally, a fixed-effects analysis of covariance model, with treatment and injection site as categorical covariates, and baseline weight as a continuous covariate fitted on the log scale and including an interaction term between treatment and injection site will be performed for the primary PK endpoints.

User and device errors will be summarized using appropriate descriptive statistics.

9.4. Interim Analysis

No formal interim analysis is planned; however, if recruitment is significantly slower than anticipated, then a single interim analysis may be conducted to assess variability, and which could result in a re-estimation of the sample size.

Available PK concentration data from completed participants may be inspected to support development of depemokimab PK model. No changes to the conduct of the study will be implemented as a result of these analyses.

9.5. Sample Size Determination

A total of approximately 126 (63 per treatment group) participants will be required to complete at least Week 18 of the study.

The primary aim of this study is to estimate the relative bioavailability of the autoinjector compared with the SSD. Therefore, the sample size calculation for this study is based on the number of participants needed to achieve an acceptable level of precision in the estimate of relative bioavailability.

The variability of depemokimab PK parameters (AUC and C_{max}) was informed by the depemokimab FTIH Study 205722 [GSK Document Number [2019N411063_00](#)] and the mepolizumab Phase 1 Study 204958 [GSK Document Number [2017N342446_01](#)], and is in line with results reported for monoclonal antibodies against soluble targets delivered subcutaneously.

Between CV_b of 30% was assumed for both AUC(0-inf) and C_{max}. Based on this CV_b, with a sample size of 63 participants per treatment group, the 90% CI for an estimated ratio of autoinjector versus SSD of 1.00 will be (0.92, 1.09).

In addition, assuming a within-subject correlation of 0.8 between AUC and C_{max}, and a true ratio of 1, a sample size of 63 participants will also provide 90% power to observe geometric CI of geometric mean ratio within the bioequivalence range of (0.8, 1.25) for both parameters.

Approximately 140 healthy participants will be enrolled (accounting for drop-out rate of 10% until Week 18) resulting in at least 126 evaluable participants (approximately 63 for each treatment group, 21 per injection anatomical site within each treatment group).

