4. STUDY DESIGN

4.1. Overall Design

This is a Phase 1, randomized, multicenter, open-label, parallel-group, single-dose study in healthy adult participants. A single subcutaneous dose of depemokimab will be administered via a SSD or an autoinjector.

The study will consist of a screening period, one treatment period, and a follow-up period.

Participants will be randomly assigned in a 1:1 ratio to receive 1 of 2 treatments during the treatment period as follows:

- Treatment A: a single subcutaneous dose of 100 mg depemokimab administered via a SSD
- Treatment B: a single subcutaneous dose of 100 mg depemokimab administered via an autoinjector

The randomization will be stratified by body weight (<70 kg, 70 to <80 kg, and ≥80 kg). The site of injection will be randomized in a 1:1:1 ratio to the upper arm, abdomen, or thigh. All treatments will be administered by authorized study site staff.

Participants will be screened within 30 days before the first dose of study intervention. Each participant will receive a single subcutaneous dose of depemokimab on Day 1 and will then be observed. Participants may be discharged from the clinic after all study procedures have been completed on Day 3. Participants will return for outpatient visits and receive a follow-up telephone call approximately 211 days after study intervention administration.

Study assessments will be performed as indicated in the SoA (Section 1.3) Pharmacokinetic blood samples for the analysis of depemokimab will be collected prior to dosing on Day 1 and up to Day 183 after dosing.

Safety and tolerability will be assessed by the monitoring and recording of AEs, clinical laboratory test results, vital sign measurements, and 12-lead ECG results.

Including screening and the follow-up period, the total duration of the study is approximately 241 days.

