9.5.1. Sample Size Sensitivity

The table below provides the expected 90% CI estimates for a range of CV_b, assuming 5% difference in either direction in the ratio between autoinjector and SSD and n = 63 per treatment group.

CV _b	SDlogs	Estimated Ratio (Autoinjector/pre-filled safety syringe)	Expected Two-sided 90% CI
0.30	0.293	0.95	(0.87,1.04)
		1.00	(0.92,1.09)
		1.05	(0.96,1.15)
0.35	0.339	0.95	(0.86,1.05)
		1.00	(0.90,1.11)
		1.05	(0.95,1.16)

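### The stated 90% power for both confidence intervals to fall within 0.80–1.25 does not follow from its inputs, which give about 98%; the error is conservative and the sample size stands

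*Protocol*

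**What the plan says.** Protocol section 9.5 sets the size of the study: "A total of approximately 126 (63 per treatment group) participants will be required to complete at least Week 18 of the study". It bases that number on the precision of the estimated ratio. With a between-subject CV of 30% for both AUC(0-inf) and Cmax, an estimated ratio of 1.00 is expected to carry a 90% CI of (0.92, 1.09).

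The section then adds a power statement, which takes the true ratio as 1 and the correlation between the two parameters as 0.8: "a sample size of 63 participants will also provide 90% power to observe geometric CI of geometric mean ratio within the bioequivalence range". The range in question runs from 0.8 to 1.25, and the claim covers AUC and Cmax together. SAP section 5 has the same sentence.

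The comparison that this power refers to is in Protocol section 9.1. No formal hypothesis is tested there, but an additional assessment is made by "comparing observed 90% CI of geometric mean ratio to the standard bioequivalence reference range of 0.8 to 1.25".

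Protocol section 9.5.1 and SAP section 5.1 tabulate expected CIs for CVs of 30% and 35% and ratios of 0.95, 1.00 and 1.05. They give no power.

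**The concern.** Everything needed to compute the power is in the documents, and the neighbouring figures follow exactly from the same inputs. A colleague or regulator who recomputes the power will not obtain 90%. It is the only power figure in either document, and it supports the planned comparison with the bioequivalence range. It should therefore either be correct for the stated inputs or show the inputs from which it came.

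What is at stake is the accuracy and traceability of the sample size section. The trial's capacity to answer its question is not in doubt, because the true figure is higher than the stated one.

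**Working it through.** **Inputs**
- CV 30% for both parameters, 63 per group, true ratio 1, correlation 0.8: Protocol section 9.5.
- Parallel groups, 1:1 allocation: Protocol section 4.1.
- Two-sided 90% CIs, range 0.80 to 1.25: Protocol section 9.1. On the log scale the limits are ±ln(1.25) = ±0.2231.

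**Step 1: reproduce the plan's precision figure**
- Log-scale SD = sqrt(ln(1 + 0.30²)) = 0.2936 (the sensitivity table shows 0.293).
- SE of the log ratio = 0.2936 × sqrt(2/63) = 0.0523.
- t(0.95, 124 df) = 1.657, so the half-width is 1.657 × 0.0523 = 0.087.
- Expected 90% CI at ratio 1.00 = exp(±0.087) = (0.917, 1.091), which matches the stated (0.92, 1.09).
- The other sensitivity rows also match. For example, CV 35% at ratio 1.00 gives (0.904, 1.106) against (0.90, 1.11).
- Enrolment matches too: 126/0.9 = 140.

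The SD, the per-group reading of 63 and the CI method are therefore those of the plan.

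**Step 2: power for one parameter**
- Normal approximation: 2Φ(0.2231/0.0523 − 1.645) − 1 = 0.991.
- Integrating over the variance estimate with 124 df: 0.9906.

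**Step 3: joint power for both parameters**
- Bounds that hold for any correlation: joint power cannot exceed 0.9906 and cannot fall below 1 − 2 × (1 − 0.9906) = 0.981. A figure of 90% is excluded before any simulation.
- Simulation with correlation 0.8 (400,000 draws, bivariate normal mean differences, Wishart covariance): 0.984.
- With correlation 0 it is 0.981.

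**Step 4: the group size that gives 90% at these inputs**
- Joint power is 89.1% at 42 per group, 90.1% at 43 and 90.9% at 44.

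**Step 5: other readings of the sentence (correlation 0.8)**

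| Reading | Joint power |
|---|---|
| As stated, 63 per group | 98.4% |
| 63 as the total (31 + 32) | 73.7% |
| 70 per group (all 140 enrolled) | 99.2% |
| Log-scale SD taken as 0.30 directly | 98.0% |
| Three df lost to covariates | 98.5% |
| 95% CIs instead of 90% | 96.3% |
| CV 35%, ratio 1.00 | about 93% |
| CV 30%, ratio 0.95 / 1.05 | about 92% / 93% |
| CV 35%, ratio 0.95 / 1.05 | about 83% / 84% |
| CV 37%, ratio 1.00 | about 90% |

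About 90% appears only with inputs that the section does not state, such as a CV near 37%. That does not show where the figure came from; the documents do not say.

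**The case against.** The strongest defence is that a design with 98% power also has 90% power, and that power is often quoted as the threshold met. Read as at least 90%, the sentence is true. But the text does not say at least, and the figures around it are direct consequences of the inputs, so a reader will take this one the same way. The power sentence also does not restate its CV. Thirty per cent is the natural reading, and 35%, the only other CV in the plan, gives about 93% at a ratio of 1.

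The second defence stands in full: the error has no consequence for the design. The sample size rests on precision, which reproduces, and the power remark is supplementary to it.

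A reader might go further in three ways that the documents do not support:
- **That the study is underpowered.** The opposite holds at the stated inputs.
- **That the 90% figure could drive a cut to about 43 per group.** Protocol section 9.4 says that, if recruitment is significantly slower than expected, "a single interim analysis may be conducted to assess variability, and which could result in a re-estimation of the sample size". Neither that section nor SAP section 4.7 ties such a look to the 90% figure, and the only stated basis for the sample size is CI width. The figure of 43 shows how far the stated power is from its inputs. It is not a forecast.
- **That the sentence conceals the loss of power at other ratios or CVs.** It states its condition of a true ratio of 1 openly. The sensitivity table varies CV and ratio for CI width, which is the criterion that sets the size, and all six tabulated intervals lie within 0.8 to 1.25. The plan is not obliged to tabulate power for an assessment that is not a formal test.

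**Conclusion.** The 90% is wrong as written in both documents. At 63 per treatment group, CV 30%, true ratio 1.00, correlation 0.8 and two-sided 90% CIs, the probability that both intervals lie within 0.80 to 1.25 is about 98%, some 8 percentage points above the stated value. The assumed correlation hardly matters, since any value leaves the joint power between 98.1% and 99.1%. The result rests on log-normal parameters, equal variances in the two groups and 126 evaluable participants.

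This is a conservative misstatement in a supplementary sentence. The number of participants, the primary analysis and the planned interpretation are unaffected.

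**What to change.** In Protocol section 9.5 and SAP section 5, replace the power statement with one that gives about 98% power with 63 participants per treatment group, at a CV of 30%, a true ratio of 1.00 and a correlation of 0.8. If 90% was meant under other assumptions, state those inputs instead. Either way, write per treatment group after 63 and name the CV in the sentence.

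Optionally, add a power column to the sensitivity tables in Protocol section 9.5.1 and SAP section 5.1. At CV 30% the entries would be about 98% at ratio 1.00 and 92–93% at 0.95 or 1.05. At CV 35% they would be about 93% at ratio 1.00 and 83–84% at 0.95 or 1.05.

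The cost is a wording change in two documents. The sample size and the analysis stay as they are.
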